## Study Summary

Title	Clinical Trial of Manganese-Enhanced MRI (MEMRI) to Assess Peri-Infarct Injury
Short Title	MEMRI-DEMRI
Protocol Number	28508
Phase	Clinical study phase 2
Methodology	Open Label
Study Duration	
 
i. Screening - approximately 1-2 hours including H&P, blood work and EKG.
 
ii. Active participation - MRI study itself is approximately 1.5 hr per exam.
 
iii. Analysis of participant data takes approximately 1 hr per exam with an additional 0.5 hr per patient for tallying clinical outcomes and AEs.
 
iv. Total time estimated 3 days per patient. We expect the study to take approximately 12 months.
 

Study Center(s)	Single
Objectives	This is a first-in-human clinical translation of manganese-enhanced MRI (MEMRI) to assess the peri-infarct injury in patients with severe ischemic cardiomyopathy (ICM) , non-ischemic cardiomyopathy (NICM) and atrial fibrillation
Number of Subjects	50
Diagnosis and Main Inclusion Criteria	
 
• Patients with ischemic or dilated cardiomyopathy with an EF less than or equal to 50 or patients with paroxysmal or persistent atrial fibrillation who are at least 18 and less than 80 years of age. Only males and non-pregnant females to be included.
 

Study Product, Dose, Route, Regimen	
EVP 1001-1 (SeeMore™) Injectable  Manufacturer: University of Iowa Pharmaceuticals  IND # [REDACTED]  Dosage: 0.28 ml/kg

Duration of administration	Intravenous injectable given slowly over approximately one (1) minute
Reference therapy	Gadolinium
Statistical Methodology	Student's t-test to assess for significant difference between MEMRI and DEMRI; Pearson Correlation to assess for relationship between MEMRI and signal and cardiac function/clinical outcome

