## 1.1 Background

- This is a first-in-human clinical translation of manganese-enhanced MRI(MEMRI) to assess the peri-infarct injury in patients with patients with ischemic or dilated cardiomyopathy with an EF less than or equal to 50 or patients with paroxysmal or persistent atrial fibrillation
- and those who received stem cell therapy for these indications. The PI recently obtained an approval for an Investigational New Drug (IND # [REDACTED]) to conduct a clinical trial of MEMRI contrast agent (EVP1001-1, Eagle Vision, Downingtown, PA). Funding of this proposal will enable a clinical trial of 120 patients with ischemic or dilated cardiomyopathy with an EF less than or equal to 50 or patients with paroxysmal or persistent atrial fibrillation to evaluate the safety and efficacy of sequential acquisition of MEMRI and delayed-enhanced MRI (DEMRI) for precise tissue characterization of the peri-infarct region (PIR). This novel technique designed to integrate the biology of the viable cardiomyocytes with the anatomy of the scar will predict future cardiovascular events (CVE), in this highly morbid patient population. ICM and NICM are the primary etiology of advanced heart failure (HF) while ACM is a frequent sequela of HF. Today, HF is the leading diagnosis of hospital admission in the US. Our studies have confirmed a direct association between the presence of PIR and the occurrence of atrial and ventricular arrhythmia and remodeling, resulting in high morbidity and mortality in advanced HF. PIR has been recognized as an important substrate to trigger atrial and ventricular arrhythmias and stem cells may provide an alternative therapy for PIR. Studies employing DEMRI has identified atrial scar as the potential cause of atrial arrhythmia. This proposal contains novel hypotheses well-grounded on the following 2 innovations: (1) MEMRI for management of HF. An alternative approach is to employ manganese (Mn2+), which targets the viable myocardium. Mn2+ is specific to the L-type calcium channels and complements the non-viable scar delineated by DEMRI. The dual MEMRI-DEMRI approach will, therefore, identify the viable and, potentially, salvageable cardiomyocytes outside the core infarct zone but inside the PIR. Our recently published study demonstrated that an overlap of DEMRI and MEMRI signal denoted a significant number of live cardiomyocytes (MEMRI-positive) within the non-viable (DEMRI-positive) region. This innovation will profoundly impact the clinical management of the advanced HF patients and AA patients including atrial fibrillation. EVP1001-1 allows highly effective intracellular targeting of viable cardiomyocytes with high level of safety and unique magnetic properties. (2) Assessment of therapeutic response using MEMRI. EVP1001-1 is rapidly transported, intra-cellularly, to mitochondria rich tissue such as heart, liver, and kidney, demonstrating significant enhancement indicative of cell metabolism and viability. High dose clinical safety studies of SeeMoreTM with safety index of 45-90 correspond more favorably than the widely used clinical imaging agents (10-20 for iodinated X-ray products and 20-60 for gadolinium). This specific, non-perfusion dependent distribution due to active intracellular uptake is one of the key attributes that offers real-time assessment of therapeutic response, using cardiac cellular imaging. A clinical safety trial in 6 patients have demonstrated negligible uptake in the intra-infarct region (IIR), reduced uptake in the PIR, and significantly higher uptake in the normal tissue to generate positive signal. In this trial, the mean LVEF was 32±4%. The DEMRI vs. MEMRI (scar/myocardial volume) demonstrated significantly higher measurement of the scar by DEMRI in all patients (39±11%\* vs. 16±3%, \*p<0.01) These data indicate 2 important findings: 1) significant over-estimation of the scar by DEMRI and 2) quantitative difference of the scar volume between MEMRI and DEMRI delineates the PIR. This precise characterization allows accurate assessment of the efficacy of novel therapeutic agents in restoring the PIR at both cellular and tissue levels. EVP1001-1 is a new manganese (Mn)-based intravenous imaging agent being developed to enhance magnetic resonance imaging (MRI). While Mn has long been known to have desirable magnetic and kinetic properties for MRI, use in humans was not initially possible due to cardiovascular depression and electrocardiogram (ECG) changes, including prolongation of PR and QTc intervals, associated with intravenous administration. Chelation of Mn, as had been done with gadolinium for use with MRI, provided relevant safety, but sacrificed desirable magnetic and kinetic properties. EVP1001-1 provides Mn in a form that maintains the desired magnetic and kinetic properties while overcoming the cardiovascular toxicity of Mn. EVP1001 is taken up into heart cells (primarily via addition of calcium to avoid cardiotoxic effects; please refer to patent listed below). The potential to distinguish healthy heart tissue from unhealthy heart tissue based on a specific sustained pattern of enhancement provides a basis for evaluating the performance of EVP1001-1 in heart patients. MRI offers benefits over other imaging technologies. Relative to radioactive nuclear imaging procedures, MRI is 3- dimensional, provides good soft tissue discrimination, and is of high spatial and temporal resolution. These features have been reported to identify smaller defects (e.g., subendocardial infarcts) and match angiographic results more closely than other modalities such as SPECT. It may be possible to enhance the utility of MRI for heart disease further through the use of an imaging agent that is specifically taken up into heart cells. EVP1001-1 is the only cardiac-specific agent being developed for this purpose. Unlike nuclear perfusion agents, EVP1001-1 is not radioactive and does not require special handling, shielding, transport or storage. In addition, the specific pattern of enhancement achieved in the heart muscle persists

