#### 1.4 Clinical Data to Date

This is a clinical translation of manganese-enhanced MRI (MEMRI) to assess the peri-infarct injury in patients with severe ischemic cardiomyopathy (ICM). The PI recently obtained an approval for an Investigational New Drug (IND # [REDACTED]) to conduct a clinical trial of MEMRI contrast agent (SeeMore™, Eagle Vision, Downingtown, PA). He has already completed initial pilot study of safety in 6 patients and found no adverse event. Funding of this proposal will enable a clinical trial of 60 patients with severe ICM, NICM and atrial arrhythmia (AA) and those undergoing stem cell therapy to evaluate the safety and efficacy of sequential acquisition of MEMRI and delayed-enhanced MRI (DEMRI) for precise tracking of stem cell engraftment and tissue characterization of the peri-infarct region (PIR). This novel technique designed to integrate the biology of the stem cells delivered into the myocardium and their regional effects on myocardia viability will elucidate the mechanism underlying clinical outcome in this highly morbid patient population. ICM is the primary etiology of advanced heart failure (HF), the leading diagnosis of hospital admission in the US. Our studies have confirmed a direct association between the presence of PIR and the occurrence of ventricular arrhythmia and LV remodeling, resulting in high morbidity and mortality in advanced HF. PIR has been recognized as an important substrate to trigger ventricular arrhythmias and clinical trials have demonstrated that the revascularization of the PIR result in lower incidence of CVE. In order to reliably evaluate the role of the PIR, we conducted 3 published clinical studies employing DEMRI, the current gold standard, to assess myocardial injury. These studies confirmed that the presence of ischemia, scar, and/or tissue heterogeneity in the PIR predicted future CVE. Although transmurality of DEMRI scar is used to predict functional recovery and improved survival after revascularization, DEMRI does not evaluate direct myocardial viability due to its nonspecific distribution within the extracellular space. The majority of the discrepancy lies within the heterogeneous PIR, resulting in overestimation of the non-viable infarct. To date, there is no established imaging strategy to identify the viable and, potentially, salvageable cardiomyocytes within the PIR. In order to address these issues, this proposal contains novel hypotheses well-grounded on the following 2 innovations: 1) MEMRI for management of HF. An alternative approach is to employ manganese ( $\text{Mn}^{2+}$ ), which targets the viable myocardium.  $\text{Mn}^{2+}$  is specific to the L-type calcium channels and complements the non-viable scar delineated by DEMRI. The dual MEMRI-DEMRI approach will, therefore, identify the viable and, potentially, salvageable cardiomyocytes outside the core infarct zone but inside the PIR. Our recently published study demonstrated that an overlap of DEMRI and MEMRI signal denoted a significant number of live cardiomyocytes (MEMRI-positive) within the non-viable (DEMRI-positive) region. This innovation will profoundly impact the clinical management of the advanced HF patients and AA patients including atrial fibrillation. EVP1001-1 allows highly effective intracellular targeting of viable cardiomyocytes with high level of safety and unique magnetic properties. 2) Assessment of therapeutic

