
response using MEMRI. EVP1001-1 is rapidly transported, intra-cellularly, to mitochondria rich tissue such as heart, liver, and kidney, demonstrating significant enhancement indicative of cell metabolism and viability. High dose clinical safety studies of SeeMore™ with safety index of 45-90 correspond more favorably than the widely used clinical imaging agents (10-20 for iodinated X-ray products and 20-60 for gadolinium). This specific, non-perfusion dependent distribution due to active intracellular uptake is one of the key attributes that offers real-time assessment of therapeutic response, using cardiac cellular imaging. A clinical safety trial in 6 patients have demonstrated negligible uptake in the intra-infarct region (IIR), reduced uptake in the PIR, and significantly higher uptake in the normal tissue to generate positive signal. In this trial, the mean LVEF was 32±24%. The DEMRI vs. MEMRI (scar/myocardial volume) demonstrated significantly higher measurement of the scar by DEMRI in all patients (39±11%\* vs. 16±3%, \*p<0.01).

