## 7 Statistical Plan

### 7.1 Sample Size Determination

The total number of 0 patients will power this study adequately, however as we have extended the protocol to include the atrial fibrillation participants (and extra 60 pts) the difficulty in imaging the atria, coupled with the thin atrial walls, means that we expect a difference in DEMRI volume of 40 (+ or - 20) in participants with early disease and 60 (+ or - 20) in participants with advanced disease. Accordingly, 60 participants will be needed for the additional cohort. Our published pre-clinical study in 13 swine demonstrated the infarct volume percentage difference of 9% between MEMRI and DEMRI ( $p<0.001$ ). This difference will enable significant delineation of the changes in the peri-infarct viability between the cell therapy and control arms. The preliminary porcine data presented above demonstrated a mean of 100% increase in the CNR of the peri-infarct region and a mean of 50% decrease in the scar volume, suggesting robust MEMRI signal detection of stem cell engraftment and increased peri-infarct viability. Furthermore, the clinical trial in 6 ICM patients demonstrated significant difference in the infarct volume between MEMRI defect and DEMRI enhancement. This difference between MEMRI and DEMRI represents PIR assuring reliable detection of the PIR. Employing these data, in order to detect a mean difference of 20% in MEMRI signal of stem cell engraftment and MEMRI-DEMRI signal of peri-infarct viability with a standard deviation of 5%, the t-test sample size calculation in this study has 90% power at the alpha 0.05 significance level, assuming an equal variance between the two distributions.

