### 7.2 Statistical Methods

Student's t-test to compare MEMRI and DEMRI measurement of the infarct and viable myocardium. Pearson's correlation to generate any association between stem cell engraftment/peri-infarct viability and functional restoration and/or clinical outcome.

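### Section 7.2 relates peri-infarct viability to function and outcome without DEMRI scar in the model, so a significant correlation would not show that manganese adds information beyond gadolinium

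*Combined protocol and SAP*

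**What the plan says.** Section 7.2 names two analyses. One is a t-test comparing the MEMRI and DEMRI measurements. The other is "Pearson's correlation to generate any association between stem cell engraftment/peri-infarct viability and functional restoration and/or clinical outcome". No regression, partial correlation, covariate or comparison with DEMRI scar alone appears anywhere in the document.

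The imaging variable is not defined in 7.2. Section 1.1 says that the "quantitative difference of the scar volume between MEMRI and DEMRI delineates the PIR", and section 7.1 says "This difference between MEMRI and DEMRI represents PIR assuring reliable detection of the PIR" and plans on a "MEMRI-DEMRI signal of peri-infarct viability with a standard deviation of 5" percent. These point to the difference between the two scar volumes. The Study Summary describes the same analysis differently, as "Pearson Correlation to assess for relationship between MEMRI and signal and cardiac function/clinical outcome", which points to MEMRI signal.

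On what is already known from gadolinium imaging, section 1.4 says of the sponsor's DEMRI studies: "These studies confirmed that the presence of ischemia, scar, and/or tissue heterogeneity in the PIR predicted future CVE".

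**The concern.** A difference between two measurements carries each of its components. If DEMRI scar varies much more between patients than the MEMRI defect does, the difference ranks patients largely as DEMRI scar ranks them. Section 1.4 gives reason to expect DEMRI findings to relate to outcome. An association with the difference could then arise from the gadolinium scan alone.

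The correlation is the only named analysis that links the imaging to function or to the event follow-up in Specific Aim 2. Every patient receives the investigational agent in addition to gadolinium, so the question a reader will ask of this analysis is what the manganese scan adds. An unadjusted correlation cannot answer it.

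**Working it through.** **The plan's own figures.** No sample size, power or target correlation is stated for the Pearson analysis; the 90% power in 7.1 belongs to the t-test and is not used here. The pilot figures in sections 1.1 and 1.4 are 39±11% (DEMRI) and 16±3% (MEMRI), n=6, p<0.01. Read as SDs they agree with that p-value: a paired t-test gives p between 0.0009 and 0.007 for between-scan correlations from 1 down to −0.5. Read as standard errors, the smallest possible p is 0.035. So ± is taken as an SD.

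**Step 1: how closely the difference follows DEMRI scar.** Let D be DEMRI scar, M the MEMRI defect, P = D − M, and ρ the between-scan correlation, which the documents do not give.

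corr(P, D) = (sD − ρ·sM) / √(sD² + sM² − 2ρ·sD·sM)

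This is smallest at ρ = sM/sD, where it equals √(1 − (sM/sD)²).

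- Pilot SDs 11 and 3: the minimum is √(1 − 9/121) = 0.962, at ρ = 0.27. At ρ = 0 it is 11/√130 = 0.965, and at ρ = 0.9 it is 8.3/8.40 = 0.988. Whatever ρ is, D explains at least 0.962² = 92.6% of the variance of P.
- Uncertainty of the pilot ratio: the variance ratio is 121/9 = 13.44 and the 97.5% point of F(5,5) is 7.146. The approximate 95% interval for the variance ratio is 1.88 to 96, so the SD ratio is 1.4 to 9.8 (treating the two SDs as independent). At the lower limit the minimum is √(1 − 1/1.88) = 0.68.
- Equal variances, as 7.1 assumes: corr(P, D) = √((1 − ρ)/2), which is 0.71 at ρ = 0, 0.50 at ρ = 0.5 and 0.22 at ρ = 0.9.

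**Step 2: what the unadjusted test does when MEMRI adds nothing.** Let function depend on D only, with correlation b. Then corr(P, function) = b × corr(P, D). By Fisher's z, the two-sided 5% test is significant with probability close to Φ(√(n − 3)·atanh(r) − 1.96). Example with the pilot SDs, b = 0.3 and n = 50: r = 0.3 × 0.962 = 0.289, 6.856 × 0.297 = 2.04, and Φ(0.08) = 53%.

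The documents give no value of b, so 0.3 to 0.5 is an assumed range. At n = 50:

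| corr(P, D) | b = 0.3 | b = 0.4 | b = 0.5 |
|---|---|---|---|
| 0.96 (pilot SDs) | 53% | 79% | 95% |
| 0.68 (lower limit of SD ratio) | 29% | 48% | 68% |
| 0.50 (equal variances, ρ = 0.5) | 18% | 28% | 42% |

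The document also gives sample sizes of 60 (section 7.3) and 120 (sections 1.1 and 4.3). With the pilot SDs the ranges there are 61–98% and about 90–100%.

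**Step 3: the same null case with DEMRI scar held fixed.** In 40,000 simulated trials per setting, the partial correlation of P with function given D was significant in 5% throughout. The unadjusted rates agreed with the table to within about 1 to 2 percentage points.

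**Step 4: the price.** The partial correlation detectable with 80% power is tanh((1.96 + 0.84)/√(n − 4)): 0.39 at n = 50, 0.36 at n = 60 and 0.25 at n = 120.

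**The case against.** The strongest objection is that the correlated variable is inferred. Section 7.2 leaves it undefined, the Study Summary names MEMRI signal, and the preclinical sections quantify MEMRI by signal- or contrast-to-noise ratio. For MEMRI signal, or for the stem cell engraftment half of the sentence, the bounds above do not apply. This stands, and the point is conditional on the difference reading. DEMRI scar would still be missing under the other readings, so added value would still go untested.

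A reader might infer that the PIR measure is established to be almost a copy of DEMRI scar. The documents do not support that. The 0.96 is a point estimate from 6 ischemic patients. The trial also enrols patients with dilated cardiomyopathy and atrial fibrillation, for whom no MEMRI spread is given, and 7.1 assumes equal variances, under which the tie is looser.

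A reader might also infer that the trial would declare success on this correlation. No success criterion rests on it. Sections 3.1 and 3.2 base primary efficacy on the presence or absence of infarction and ischemia, event follow-up is the secondary aim, and the wording of 7.2 is exploratory. The accuracy claims in sections 1.1 and 1.4 concern imaging accuracy, not prognosis beyond DEMRI.

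Two further extensions do not hold. Unequal variances make the difference rise with scar burden, but that does not invalidate a t-test of whether the scans differ on average. And if the PIR is defined instead as tissue positive on both scans, the bound for D − M does not carry over without further assumptions.

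Finally, the statement in section 1.4 covers ischemia, scar and/or heterogeneity. It does not isolate scar volume and says nothing about function, so the 0.3 to 0.5 range remains an assumption.

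**Conclusion.** The concern holds in conditional form. If peri-infarct viability means the MEMRI-DEMRI difference, as sections 1.1 and 7.1 indicate, the planned correlation cannot separate a contribution from manganese from a restatement of DEMRI scar. With n=50 and an assumed scar-function correlation of 0.3 to 0.5, the chance of a significant result when MEMRI adds nothing is about 53–95% at the pilot SDs. It is 29–68% at the lower limit of their ratio, and 18–42% under equal variances with an assumed between-scan correlation of 0.5. Each compares with 5% after adjustment. The size therefore depends heavily on a ratio the pilot measures poorly and, under equal variances, on an unreported between-scan correlation. The need for the adjustment does not depend on the pilot SDs. As this is a secondary association analysis, the change should be made but is not critical to the trial.

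**What to change.** In section 7.2:

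- State that the imaging variable is the MEMRI defect volume or the MEMRI-DEMRI difference, and align the Study Summary with it. Once DEMRI scar is in a linear model the two choices give the same test, because D − M adds only M.
- Fit function (or outcome) on DEMRI scar volume, then add the MEMRI term.
- Base any statement of added value on that term, by partial correlation or likelihood-ratio test.
- Keep the unadjusted Pearson correlation as descriptive if wanted.

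Section 3.1 plans both scans for every patient, so no new imaging is needed and the change is one of wording. The cost is precision: the adjusted interval is wider and significance less likely. At n=50 only a partial correlation of about 0.39 is detectable with 80% power, and the plan should say so.

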## **2 Study Objectives**

This is a first-in-human clinical trial of combined manganese-enhanced MRI(MEMRI) and delayed-enhanced MRI(DEMRI) to determine reliable detection and clinical significance of peri-infarct injury in both the ventricles and atria. An IND approval was obtained to utilize EVP1001-1 to assess peri-infarct injury in patients with ischemic or dilated cardiomyopathy atrial fibrillation and those who undergo stem cell therapy for these indications. In preparation for a Phase I/II clinical trial, an initial safety study of 6 patients has been completed and no adverse events were observed. This proposal will enable a clinical trial of 50 patients to evaluate the safety and efficacy of MEMRI-DEMRI to characterize peri-infarct injury.

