## **4 Subject Selection and Withdrawal**

### **4.1 Inclusion Criteria**

All subjects to be entered must:

- be at least 18 years of age and less than 80 years
- if female, be non-pregnant as evidenced by a serum pregnancy test and using a medically-approved method of birth control, or post-menopausal or surgically sterile
- provide written informed consent after having received oral and written information about the study
- patients with ischemic or dilated cardiomyopathy with an EF less than or equal to 50 or patients with paroxysmal or persistent atrial fibrillation
- Have completed the MRI checklist and do not have exclusions to having an MRI
- 

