### **4.2 Exclusion Criteria**

- have a positive pregnancy test (females)
- received an investigational drug or device within 30 days prior to administration of EVP1001-1

- have known hypersensitivity to ondansetron or other selective serotonin 5HT3 receptor blockers
- are taking a digitalis preparation or calcium channel blocker within 30 days to MRI
- Contraindication to receiving metoprolol
- have a history of torsades or prolonged QT/QTc interval (QTc > 470 msec)
- have NYHA Grade IV heart failure or EF less than 25
- have abnormal liver function tests or a history of liver disease (2 times upper limits of normal)
- have stage 11 hypertension (Systolic Blood Pressure > 140 or Diastolic BP > 90 consistently at baseline)
- have abnormal baseline potassium or calcium (outside normal reference ranges)
- hemoglobin less than 10 g/dl
- Have a history of ventricular arrhythmia per stress test or monitoring
- No recent cardiac intervention within 90 days (CABG, Valve, PTCA)
- No recent CHF, MI or Angina within 60 days
- Conduction disease (QRSd >120 msec or Sick Sinus Syndrome.)
- No cardiac implantable device
- Weight not to exceed 300 kgs and/or chest circumference .36cms
- 

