### 7.3 Subject Population(s) for Analysis

We expect to enroll 60 patients with various cardiomyopathies including NICM, ICM, and ACM (dilated cardiomyopathy, ischemic cardiomyopathy, and atrial cardiomyopathy). Our goal is to demonstrate improved sensitivity and specificity of identifying viable myocardium and PIR in the ventricles and atria in various cardiac patients to help improve clinical management

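### The planned correlation of MEMRI signal with cardiac function has no cohort term: if mean EF and the lesion measure both differ between cardiomyopathy and AF patients, a pooled coefficient can be significant with no association inside either cohort

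*Combined protocol and SAP*

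**What the plan says.** The method is one line in Section 7.2, a Pearson correlation for "any association between stem cell engraftment/peri-infarct viability and functional restoration and/or clinical outcome". The Study Summary gives a parallel line: "Pearson Correlation to assess for relationship between MEMRI and signal and cardiac function/clinical outcome". Neither mentions a stratum, a covariate or separate coefficients. The two lines also name different targets: restoration of function in 7.2, cardiac function in the Summary. Neither names EF.

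Section 7.3 sets out a single analysis population: "We expect to enroll 60 patients with various cardiomyopathies including NICM, ICM, and ACM".

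Entry rules differ by cohort. Section 4.1 admits "patients with ischemic or dilated cardiomyopathy with an EF less than or equal to 50 or patients with paroxysmal or persistent atrial fibrillation", so the EF ceiling belongs to the cardiomyopathy branch only. Section 4.2 excludes patients who "have NYHA Grade IV heart failure or EF less than 25", and this applies to everyone. Cardiomyopathy EF therefore lies between 25 and 50, while AF EF is 25 or above.

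Section 7.1 treats AF as an additional cohort, cites the thin atrial walls, and expects DEMRI volumes of 40 (±20) in early and 60 (±20) in advanced disease. The six-patient pilot (Sections 1.1 and 1.4) reports scar as a share of myocardial volume: 39±11% by DEMRI and 16±3% by MEMRI.

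The sample size is not consistent. Section 2 says "This proposal will enable a clinical trial of 50 patients", Section 1.1 says "Funding of this proposal will enable a clinical trial of 120 patients", and Section 7.3 says 60.

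**The concern.** The entry rule can tie cohort membership to the function variable, because one cohort is capped on EF and the other is not. The imaging measure may also depend on cohort, since ventricular scar and atrial wall are different targets. When two variables each shift with a third, a correlation that ignores the third picks up the distance between the group means. It then answers whether cardiomyopathy patients differ from AF patients. The plan asks whether viability tracks function among comparable patients.

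Pearson's correlation is the only method the plan names for linking MEMRI to function or outcome. A significant coefficient would be read as evidence of clinical relevance, and it could arise with no such relation within either cohort. The problem is separate from whether patients without an infarct can have a peri-infarct region, and it would remain if the lesion measure were valid in every cohort.

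**Working it through.** The plan gives no sample size, power or expected coefficient for the correlation, so there is no figure to reproduce. The 60 AF participants in Section 7.1 are tied to expected DEMRI volumes in early and advanced disease and do not enter here.

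**Step 1: what counts as significant.** The critical value is |r| = t/√(N−2+t²), with t the two-sided 5% point on N−2 degrees of freedom. It is 0.279 at N=50, 0.254 at N=60 and 0.179 at N=120.

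**Step 2: pooled r when the within-cohort correlation is zero.** With AF fraction p, cohort mean gaps Δx (lesion) and Δy (EF), and average within-cohort variances σx² and σy²:

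r = p(1−p)ΔxΔy / √{[σx² + p(1−p)Δx²][σy² + p(1−p)Δy²]}

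If Δx or Δy is zero, r is zero. Different EF limits are therefore not enough alone; both means must differ.

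**Step 3: inputs.**
- From the documents: the EF limits; a pilot DEMRI minus MEMRI gap of 39−16 = 23 points; SD 11 (pilot DEMRI, standing in for the SD of the difference); SD 20 (AF, Section 7.1).
- Assumed: cardiomyopathy EF 36 (SD 8) cut to 25–50; AF EF mean 45 to 55 (SD 7); AF lesion difference 18, 13 or 5, giving gaps of 5, 10 or 18; equal cohorts (p = 0.5).

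The EF cut points are at z = −1.375 and 1.75. The cut mean is 36 + 8×(0.155−0.086)/0.875 = 36.6. The cut variance is 64×(1−0.416−0.006) = 37. Averaged with 7² = 49 for AF, σy² = 43.

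**Step 4: the two extremes at SD 11 (σx² = 121).**
- Gap 18, AF EF 55 (Δy = 18.4): 0.25×(−18)×18.4 = −82.8. Denominator √[(121+81)(43+84.6)] = √25,775 = 160.5. r = −0.52.
- Gap 5, AF EF 45 (Δy = 8.4): 0.25×(−5)×8.4 = −10.5. Denominator √[(121+6.25)(43+17.6)] = 87.8. r = −0.12.

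The first is well beyond 0.279. The second is short of it, but it still shifts the null distribution.

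**Step 5: simulated rate of p<0.05, 25+25 patients, zero within-cohort correlation.** Ranges are over AF EF 45–55 and gaps of 5–18.

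| Lesion SD | Pooled |
|---|---|
| 11 in both cohorts | about 12% to 99% |
| 20 in AF only | about 9% to 85% |
| 20 in both cohorts | about 7% to 70% |
| Equal lesion means | about 5% to 6% |

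After centring each variable on its cohort mean (df = N−3), the rate is about 4% to 7% throughout. With 60+60 and SD 11, the pooled rate is 26% to 100%.

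**Step 6: a second set of distributions.** Cardiomyopathy EF is uniform on 25–50, AF EF is normal cut to 25–75, the cohorts are equal in size, and the lesion gap is d standard deviations.

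| AF EF mean (SD) | d | N=50 | N=60 | N=120 |
|---|---|---|---|---|
| 45 (10) | 0.5 | 11% | 12% | 21% |
| 45 (10) | 1 | 28% | 32% | 56% |
| 55 (8) | 0.5 | 26% | 29% | 52% |
| 55 (8) | 1 | 72% | 79% | 98% |

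The adjusted rate is 4.4% to 5.5% in every scenario. With equal mean EF (37.5 in both cohorts), the pooled rate is 5% to 6%. With AF at 20% to 30% of 50 patients, AF EF 55 and d=1, it is still 45% to 62%.

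**Step 7: the DEMRI figures in the documents.** Assume that the pilot's 39 (SD 11) and Section 7.1's AF values (SD 20) are the same measure. At 25+25 and AF EF 45 to 55, an AF mean of 40 gives 5% to 6%. A mean of 50 gives 23% to 48%, and a mean of 60 gives 58% to 94%. Here r is positive, so the artefact can take either sign.

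**The case against.** Several stronger readings are tempting, and the documents do not support them.

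- **That the plan commits to one pooled coefficient.** It never says so. Section 7.1 gives AF its own expected values and its own number, so separate coefficients are compatible with the text. What stands is that nothing calls for them, and that Section 7.3 describes one mixed population.
- **That different EF limits produce the artefact by themselves.** They do not. With equal mean EF or equal lesion means, the pooled rate is nominal.
- **That AF lesions are known to be smaller.** No AF MEMRI-DEMRI difference is given. The only AF lesion figures are DEMRI 40 and 60, against 39 in the pilot. They do not show smaller lesions, and the units may not match.
- **That the EF rule selects on every outcome in 7.2.** It acts on baseline function. Its effect on a change score or on cardiovascular events is less direct, and the simulations do not cover either.
- **That nothing else links MEMRI to outcome.** Section 3.2 also plans a comparison with patient outcomes, but names no method.

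Two objections to the remedy also stand. The entry categories are joined by an or and can overlap, so cohort needs an allocation rule. And because cohort is partly defined by EF, adjustment also removes any genuine between-cohort association. ICM and NICM share the same EF limits, so the entry-rule argument does not itself require separating them.

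**Conclusion.** The point holds conditionally. Followed as written, the plan permits a pooled Pearson coefficient that can be significant with no within-cohort association, provided mean EF and the lesion measure both differ between cardiomyopathy and AF patients. The entry criteria make the first plausible, and the different imaging target makes the second plausible. Neither is established by the documents.

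The size therefore rests on assumed AF EF, AF lesion values and cohort mix. It is also sensitive to the SD: moving from 11 to 20 in both cohorts lowers the upper end from about 99% to about 70% at 25+25. No single figure should be quoted as the expected error rate. What is stable is that the pooled rate departs from 5% when both means differ, grows with N, and returns to about 4% to 7% after cohort adjustment. The conclusion applies to baseline cardiac function, as worded in the Study Summary. It should be corrected, given the low cost.

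**What to change.** In Section 7.2, and to match in the Study Summary:

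1. Name the function variable, and say whether it is baseline EF or a change.
2. Make the analysis a partial Pearson correlation adjusted for entry cohort, at minimum cardiomyopathy versus AF.
3. State in advance how a patient with both conditions is allocated.
4. Report each within-cohort coefficient with its 95% CI.
5. State that no conclusion rests on the unadjusted pooled coefficient.

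This needs a few sentences and no new data beyond the allocation rule. It costs one degree of freedom with two cohorts, or two if ICM and NICM are separated. A genuine between-cohort association would no longer count as evidence. If the cohorts turn out alike on either variable, almost nothing is lost.
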